#### 4.4.4 Duration of Response

##### 4.4.4.1 RECIST Duration of Response (DoR) - Secondary Objective

The Duration of Response (DoR) is defined as the time (in months) from the first evidence of confirmed objective response (CR or PR) to the event or censoring date.

$$DoR \text{ (months)} = \frac{(date \text{ of event or censoring for DoR} - first \text{ date of PR or better}) + 1}{30.4375}$$

An event is defined as the first documentation of progression disease (disease progression assessed based on tumor assessment or clinical progression) or death due to any cause, whichever occurs earlier.

The rules for censoring cases are defined as follows:

If a subject is discontinued or lost to follow up before reporting an event will be censored at the date of the last tumor assessment documenting the absence of PD.

Subjects who start other systemic anti-cancer therapy before an event will be censored at the date of the start of this therapy.

Subjects who die or progress during the follow up period after ≥2 consecutive missed from the last tumor assessment visits will be censored at the date of the last tumor assessment before the tumor assessment of progressive disease or death.

The censoring and event date rules for Duration of Response are presented below.

**Table 5 Event and censoring dates for DoR analyses**

Events scheme:

Scenario	Date of event
Objective progression.	First date at which progression criteria are met.
Death due to any cause.	Date of death.
Non-objective progression but discontinuation of treatment due to clinical progression.	Date the last tumor assessment before the clinical progression (if any).  In case of not having any tumor assessment, the date of clinical progression should be considered.

Censoring scheme:

Scenario	Date of censoring
PD after 2 or more missed tumor assessments during the follow up period from the last tumor assessment	Date of the last tumor assessment before the event.
No PD and no Death.	Date of last tumor assessment documenting the absence of PD.

Receive any systemic therapy after treatment discontinuation.	Date of last tumor assessment documenting the absence of PD before starting systemic therapy
---	--

DoR analysis will be calculated for subjects with confirmed CR or PR as Best Overall Response.

#### 4.4.5 Progression-Free survival

##### 4.4.5.1 RECIST progression-free survival (PFS)-Exploratory Objective

The Progression-Free Survival (PFS) is defined as the time (in months) from the first administration of APX005M to the event or censoring date.

$$PFS \text{ (months)} = \frac{\text{(date of event or censoring for PFS} - \text{date of first APX005M dose}) + 1}{30.4375}$$

An event is defined as the first documentation of progression disease (disease progression assessed based on tumor assessment or clinical progression) or death due to any cause, whichever occurs earlier.

The rules for censoring cases are defined as follows:

If a subject is discontinued or lost to follow up before reporting an event will be censored at the date of the last tumor assessment documenting the absence of PD.

Subjects who start other systemic anti-cancer therapy before reporting an event will be censored at the date of the start of this therapy.

Subjects who die or progress during the follow up period after  $\geq 2$  consecutive missed from the last tumor assessment visits will be censored at the date of the last tumor assessment before the tumor assessment of progressive disease or death.

The censoring and event date options to be considered for PFS are listed below.

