**Table 6 Event and censoring dates for PFS analyses**

Events scheme:

Scenario	Date of event
Objective progression.	First date at which progression criteria are met.
Death.	Date of death.
Non-objective progression but discontinuation of treatment by clinical progression.	Date the last tumor assessment before the clinical progression (if any).  In case of not having any tumor assessment, the date of clinical progression should be considered.

Censoring scheme:

Scenario	Date of censoring
No tumor assessment after the baseline.	Date of the first dose.
PD after 2 or more missed tumor assessments during follow up period.	Date of the last tumor assessment before the event.
No PD and no Death.	Date of last tumor assessment documenting the absence of PD.
Receive any systemic therapy after treatment discontinuation.	Date of last tumor assessment documenting the absence of PD before starting systemic therapy

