#### 4.4.5.2 iRECIST progression-free survival (iPFS)-Exploratory Objective

The immune Progression-Free Survival (iPFS) is defined as the time (months) from the first administration of APX005M to the event or censoring date.

$$iPFS \text{ (months)} = \frac{(date \text{ of event or censoring for iPFS}) - date \text{ of first APX005M dose}) + 1}{30.4375}$$

An event is defined as the first documentation of iCPD, clinical progression, or death due to any cause, whichever occurs earlier.

If subjects have iUPD which is confirmed at the next assessment as iCPD, then iPFS is the time from the first administration of APX005M to the first date of iUPD that is subsequently confirmed.

The rules for censoring cases are defined as follows:

If a subject is discontinued or lost to follow up before reporting an event will be censored at the last tumor assessment documenting the absence of PD.

Subjects who start other systemic anti-cancer therapy before reporting an event will be censored at the date of the start of this therapy.

Subjects who death or progress during the follow up period after  $\geq 2$  consecutive missed from the last tumor assessment visits will be censored at the date of the last evaluable tumor assessment before the tumor assessment of progressive disease or death.

The censoring and event date rules for Duration of Response are presented below.

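### SAP text and Tables 5 to 7 give conflicting event and censoring rules for DoR, PFS and iPFS, and nothing says which governs

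*SAP*

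**What the plan says.** SAP 4.4.4.1 (DoR), 4.4.5.1 (PFS) and 4.4.5.2 (iPFS) each state event and censoring rules in prose, then again in Tables 5, 6 and 7.

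- **New systemic therapy.** The DoR prose reads: "Subjects who start other systemic anti-cancer therapy before an event will be censored at the date of the start of this therapy". The PFS and iPFS prose reads: "Subjects who start other systemic anti-cancer therapy before reporting an event will be censored at the date of the start of this therapy". The matching row in all three tables gives a different date: "Date of last tumor assessment documenting the absence of PD before starting systemic therapy".
- **Death after missed scans.** The DoR prose reads: "Subjects who die or progress during the follow up period after ≥2 consecutive missed from the last tumor assessment visits will be censored". The PFS rule opens the same way, "Subjects who die or progress during the follow up period after", and the iPFS rule ends "will be censored at the date of the last evaluable tumor assessment before the tumor assessment of progressive disease or death". Table 5's censoring row covers progression only: "PD after 2 or more missed tumor assessments during the follow up period from the last tumor assessment". Tables 6 and 7 are limited in the same way (PD and iPD). Table 5 lists "Death due to any cause" as an event on the date of death with no exception, and Tables 6 and 7 also list death without one.
- **Last response iSD (iPFS).** The prose censors subjects without an event at the last PD-free scan. Table 7's censoring scheme switches to the end-of-treatment date when the last response is iSD with no earlier iPD.
- **iUPD never confirmed (iPFS).** The prose limits events to iCPD, clinical progression and death. Table 7 adds, as an event on the first iUPD date, an iUPD after which nothing more is assessed, or one followed by a further iUPD without iCPD ever being reached.

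The sentences leading into the tables only announce them, and the one before Table 7 names the wrong endpoint (DoR). Protocol 6.3 gives no censoring rules, and protocol 6.4.3 leaves the details to the SAP.

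**The concern.** A derivation rule has to give one answer per patient. Here a programmer working from the prose and one working from the tables would both be following the SAP and would produce different datasets. For new therapy and iSD only the censoring time differs. For death after missed scans and for unconfirmed iUPD, the same patient is censored under one rule and an event under the other.

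These situations are realistic. The protocol expects later regimens to be recorded. Follow-up contact is every 3 months and may be by phone or chart review, with deaths reported. Protocol 4.3.2 waives confirmatory imaging for clinically unstable subjects.

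It is also unclear what counts as a missed scan in follow-up. Protocol 4.3 and SAP 5.3.2.1 schedule scans during treatment, while SAP 2.3 puts the 8-weekly evaluation under its Follow-up heading.

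The study is open label and small. If the choice is left until outcomes are visible, it can depend on the data. Median DoR is a named secondary objective.

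**Working it through.** **Inputs from the documents.** One month is 30.4375 days (SAP Table 2). PFS and iPFS = (event or censoring date − first dose date + 1)/30.4375, which is study day/30.4375 with first dose as day 1. DoR = (date − first response date + 1)/30.4375. Scans are every 8 weeks, so nominally on days 57, 113, 169, 225 and 281. Cohorts have 11, 11 and 18 subjects (SAP 5.1).

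**The plan's own figures.** SE = √(p(1−p)/n) gives 11.63% for 2/11 and 8.78% for 3/18, matching the stated 11.6% and 8.8%. Planned responders are 0.182 × 11 = 2.0 in Cohorts 1 and 2, and 0.167 × 18 = 3.0 in Cohort 3.

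**One patient under each rule.** All dates are assumed. The death examples further assume that treatment ended soon after day 113 and that scans remained due every 8 weeks in follow-up, so those on days 169 and 225 count as missed.

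| Scenario | Prose | Table |
|---|---|---|
| PFS or iPFS, new therapy day 100, last scan day 57 | censored, 100/30.4375 = 3.29 | censored, 57/30.4375 = 1.87 |
| PFS or iPFS, death day 260, last scan day 113 | censored, 113/30.4375 = 3.71 | event, 260/30.4375 = 8.54 |
| iPFS, iSD at last scan day 169, end of treatment day 218 | censored, 169/30.4375 = 5.55 | censored, 218/30.4375 = 7.16 |
| iPFS, iSD day 57, iUPD day 113, no later scan, alive without clinical progression | censored, 57/30.4375 = 1.87 | event, 113/30.4375 = 3.71 |
| DoR, first PR day 57, last scan day 113, new therapy day 150 | censored, 94/30.4375 = 3.09 | censored, 57/30.4375 = 1.87 |
| DoR, first PR day 57, last scan day 113, death day 260 | censored, 57/30.4375 = 1.87 | event, 204/30.4375 = 6.70 |

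**Effect on a DoR median with 3 responders (the Cohort 3 planning number).** Take the death in the last row plus two PDs at DoR 3.71 and 5.55 months.

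- Prose: the death is censored at 1.87, leaving 2 at risk. S = 0.500 at 3.71 and 0 at 5.55. The median is the midpoint where S = 0.5: (3.71 + 5.55)/2 = 4.63.
- Table: S = 0.667 at 3.71, 0.333 at 5.55 and 0 at 6.70. The median is 5.55.
- If both PDs instead fall at 1.87 (responses assumed confirmed by a 4-week scan between the 8-weekly ones), S = 0.333 at 1.87 under both rules and the median stays at 1.87.

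**Effect on PFS in an assumed cohort of 18.** Progressions: 7 on day 57, 2 on day 113, 2 on day 169. Two subjects are censored on day 281. Two start new therapy on day 85 and three die on day 225 after missed scans, all five with a last scan on day 57.

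- Prose: 11 events; S = 11/18 × 4/6 × 2/4 = 0.20 at the end.
- Table: 14 events; S = 11/18 × 7/9 × 5/7 × 2/5 = 0.14 at the end.
- The median is 3.71 months under both: S first falls below 0.5 on day 113, to 0.41 and 0.48 respectively.

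**The case against.** Only the new-therapy item plainly gives two dates for one identically named situation. The others can be read as a specific rule beside a general one. The prose on death after missed visits could be an exception to the tables' death row. Table 7's iSD clause could refine its own general rule. Table 7's iUPD rows could fill a gap, since the prose never says what to do with an iUPD that is not confirmed.

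Those readings are possible, but they need opposite precedence: prose over table for death, table over prose for iSD and iUPD. The SAP states neither.

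Several criticisms of the supporting detail do stand:

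- If scans are due only during treatment, the missed-scan rule may seldom or never apply, and the 3.71 versus 8.54 contrast would not arise. The SAP 2.3 placement is thin evidence for follow-up scanning, because the same paragraph sits in the protocol's general design section.
- A clinically unstable subject who stops for clinical progression is an event under both the prose and Table 7, so the imaging waiver is only partial support for the iUPD item.
- The prose value of 1.87 months for unconfirmed iUPD rests on reading the iUPD scan as not PD-free.
- The external tables-and-listings document named in SAP section 7 has not been seen and might carry derivation notes.

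None of this removes the contradictions in the SAP itself.

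**Conclusion.** The concern holds. The prose and Tables 5 to 7 disagree on four scenarios. New therapy and death after missed scans affect DoR, PFS and iPFS; iSD and unconfirmed iUPD affect iPFS only. Neither document says which version governs.

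In the examples the difference per patient is about 1.2 to 4.8 months (3.09 − 1.87 = 1.22 at the low end; 8.54 − 3.71 and 6.70 − 1.87, both 4.83, at the high end). Event status also changes for death and unconfirmed iUPD. These sizes rest on assumed dates, and the death examples also on follow-up scans being due.

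The consequence is bounded. Primary ORR is unaffected, no hypothesis is tested, and the median moved in one illustration and stayed put in two. With 2 or 3 planned responders per cohort, one reclassified patient can still carry weight in the secondary DoR estimate. This should be corrected, but it does not threaten the primary result.

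**What to change.** Before database lock, write one rule per scenario and make it identical in the prose and in Tables 5 to 7.

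- **New therapy:** censor at the last evaluable PD-free scan before it starts, and limit the table rows to therapy begun before any event.
- **Death after missed scans:** count it as an event in the main analysis and use censoring as a sensitivity analysis. This is consistent with, though not compelled by, protocol 6.3 (death from any cause is an event) and SAP 2.4 (which adds clinical progression and lists no exclusion of deaths). If censoring is kept as the main rule, state it in both places and list it in SAP 2.4.
- **Missed scans in follow-up:** define them as a fixed time since the last scan.
- **iSD in iPFS:** censor at the last scan.
- **Unconfirmed iUPD:** either add the Table 7 scenarios to the event definition in 4.4.5.2 or remove them from the table.
- **Lead-in to Table 7:** correct the sentence so that it names iPFS.

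The cost is SAP wording only, with no change to data collection or to patient care.

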**Table 6 Event and censoring dates for PFS analyses**

Events scheme:

Scenario	Date of event
Objective progression.	First date at which progression criteria are met.
Death.	Date of death.
Non-objective progression but discontinuation of treatment by clinical progression.	Date the last tumor assessment before the clinical progression (if any).  In case of not having any tumor assessment, the date of clinical progression should be considered.

Censoring scheme:

Scenario	Date of censoring
No tumor assessment after the baseline.	Date of the first dose.
PD after 2 or more missed tumor assessments during follow up period.	Date of the last tumor assessment before the event.
No PD and no Death.	Date of last tumor assessment documenting the absence of PD.
Receive any systemic therapy after treatment discontinuation.	Date of last tumor assessment documenting the absence of PD before starting systemic therapy

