**Note:**

If “Death” or “Clinical Progression” without confirmation has been reported as the end of treatment reason before the first scheduled tumor assessment (first tumor assessment will be evaluated approximately 8 ± 1 week following the first dose of APX005M.), the subject will be included in this population.

These subjects will be considered not evaluable for the response.

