**Table 1 Analysis population**

	Efficacy	SAF	PP
DEMOGRAPHIC CHARACTERISTICS			
-Baseline characteristics	x	x	x
-Previous treatment	x		
EFFICACY (Primary & secondary endpoints)			
Primary endpoint: -ORR by RECIST in each cohort	x		x
Secondary endpoints: -Evaluate ORR by modified RECIST 1.1 for immune-based therapeutics (iRECIST) in each cohort -Evaluate median duration of response (DOR) by RECIST in each cohort	x		
SAFETY			
Secondary objective: -Evaluate the safety of APX005M alone or in combination with radiation therapy in each cohort -Treatment exposure		x	

	Efficacy	SAF	PP
Exploratory endpoints			
- PFS (by RECIST 1.1 and iRECIST) by cohort - Duration of stable disease by cohort.	x		
Subgroup analysis			
- Subjects receiving steroids during treatment period by cohort. - LDH pre-treatment values above the upper normal range vs. below upper normal range overall and by cohort - Elevated pre-treatment LDH and prior CTLA4 overall and by cohort	x		

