**Table 7 Event and censoring dates for iPFS analyses**

Events scheme:

Scenario	Date of event
iUPD confirmed at the next assessment.	The first date of iUPD is subsequently confirmed.
If iUPD progression is not confirmed and there is no subsequent iSD, iPR, or iCR. The following scenarios may occur: 1.No further response assessments are done (Subject refusal, protocol noncompliance...). 2.The next timepoint response is iUPD, and iCPD never occurs.	The first date of iUPD is not subsequently confirmed.
Subject with non-objective progression but discontinuation of treatment by clinical progression.	Date of last tumor assessment Date of withdrawal discontinuation of treatment.
Death.	Date of death.

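### SAP Tables 6 and 7 make a subject who fails early without a scan both a PFS event and a Day 1 censored case, and do not say which rule prevails

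*SAP*

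**What the plan says.** **Censoring rows.** The censoring schemes of Table 6 (PFS) and Table 7 (iPFS) both contain the scenario "No tumor assessment after the baseline", censored at the date of the first dose. The row carries no further condition.

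**Analysis set.** SAP Table 1 assigns "PFS (by RECIST 1.1 and iRECIST) by cohort" to the Efficacy set. SAP 3.1 requires measurable disease and at least one evaluable post-baseline assessment. Its Note makes one exception: if death or unconfirmed clinical progression is the reported reason for ending treatment before the first scheduled assessment, "the subject will be included in this population".

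**Event rules.** SAP 4.4.5.1 defines a PFS event as the first documented progression ("disease progression assessed based on tumor assessment or clinical progression) or death due to any cause, whichever occurs earlier"). SAP 4.4.5.2 says for iPFS: "An event is defined as the first documentation of iCPD, clinical progression, or death due to any cause, whichever occurs earlier". SAP 2.4 lists the counting of clinical progression as a change made to the protocol analysis. Both tables date a death at the date of death. For clinical progression, Table 6 uses the last tumor assessment before it, and adds: "In case of not having any tumor assessment, the date of clinical progression should be considered". Table 7 gives "Date of last tumor assessment Date of withdrawal discontinuation of treatment" for clinical progression, with no rule for a subject who has no scan.

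Neither table says whether event rows or censoring rows come first.

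**The concern.** Within the Efficacy set, the no-scan row can reach only subjects admitted by the Note. These are people who died or progressed clinically before about week 8 and were not scanned. The SAP defines them as failures, yet the row read literally takes them out of the risk set on Day 1. That would be informative censoring: the subjects are removed because they failed early.

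The literal reading is not far-fetched. Another row of the same schemes does override an event: progression after two or more missed assessments in follow-up is censored at the last assessment before it. The row for no progression and no death states its own condition, whereas the no-scan row has none. In Table 7, that row offers the only clear date for an unscanned clinical progressor.

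At stake are the PFS and iPFS curves and the medians with 90% confidence intervals (SAP 5.3.2.3). PFS is also tabulated by LDH group within cohort (SAP 5.3.4.2), where numbers are smaller still.

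**Working it through.** **1. The plan's own figures.** The SAP gives no PFS figure. The only sample-size figures are standard errors of the response rate (SAP 5.1), and they reproduce:
- √(0.1818 × 0.8182 / 11) = 0.1163, stated as 11.6%
- √(0.1667 × 0.8333 / 18) = 0.0878, stated as 8.8%

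The planned cohort sizes, 11 and 18, are used below. The Efficacy set may differ from them.

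**2. Who the row can reach.**

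| Member of the Efficacy set | Post-baseline scan? | Event by definition? | No-scan row? |
|---|---|---|---|
| Admitted by the main rule | Yes | If progression or death occurs | No |
| Admitted by the Note, scanned at end of treatment | Yes | Yes | No |
| Admitted by the Note, not scanned | No | Yes | Yes |

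Only the last line meets the row, and everyone in it is already an event.

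**3. Effect if the censoring row is applied.** Let k of n subjects be unscanned early failures, with no other event or censoring before them.
- Coded as events: after their dates S = (n−k)/n, with n−k still at risk.
- Censored at first dose: time = (0+1)/30.4375 = 0.033 months. They leave before any event, so S = 1 with n−k at risk.
- All later factors are identical, so S(censored) / S(event) = n/(n−k).

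The documents do not give k. For an assumed k of 1 to 4:

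| k | n = 11: PFS before first scan, as events | n/(n−k) | n = 18: PFS before first scan, as events | n/(n−k) |
|---|---|---|---|---|
| 1 | 90.9% | 1.10 | 94.4% | 1.06 |
| 2 | 81.8% | 1.22 | 88.9% | 1.13 |
| 3 | 72.7% | 1.38 | 83.3% | 1.20 |
| 4 | 63.6% | 1.57 | 77.8% | 1.29 |

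With Day 1 censoring, PFS just before the first scan is 100% in every line.

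**4. Effect on the median.** Further assumptions: early failures at (28+1)/30.4375 = 0.95 months, and everyone else progressing only at 8-weekly scans, at (56+1)/30.4375 = 1.87, 3.71 and 5.55 months. About 30% to 50% of those remaining progress at each scan.

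| n, k | Share per scan | S after first scan: events / censored | Median, months: events / censored |
|---|---|---|---|
| 11, 2 | 30% | 6/11 = 54.5% / 6/9 = 66.7% | 3.71 / 3.71 |
| 11, 2 | 40% | 5/11 = 45.5% / 5/9 = 55.6% | 1.87 / 3.71 |
| 18, 3 | 30% | 11/18 = 61.1% / 11/15 = 73.3% | 3.71 / 5.55 |
| 18, 3 | 50% | 7/18 = 38.9% / 7/15 = 46.7% | 1.87 / 1.87 |

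The median moves by one scan when the two curves fall on either side of 50% at a scan, and otherwise stays put.

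**5. A related dating gap.** Table 6 does not say that the last tumor assessment excludes the baseline scan, which may be up to 21 days before treatment (Protocol 4.3). If the baseline scan counted, an unscanned clinical progressor could be dated at (−21+1)/30.4375 = −0.66 months, and the Table 6 fallback for subjects without any assessment would hardly ever apply.

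**The case against.** The strongest reply is that the SAP already points to event status. Table 6 has a sentence written for clinical progression without any assessment. Both event definitions include clinical progression and death, and SAP 2.4 adds clinical progression on purpose. The prose censoring rules for discontinuation and for new therapy apply only before an event is reported, and the no-scan row is absent from that prose. The missed-assessment rule does override events, but it says so expressly. Looking for an event first is therefore the more natural reading.

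That argument stands as far as it goes. A reader might infer that the plan does drop the worst outcomes from the curves, and the documents do not support this. They hold two conflicting instructions and do not show which one will be programmed. A reader might equally infer that the median will shift, but whether it does depends on assumed event times.

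Three further points limit the reach of the row:
- Subjects who stop before the first scheduled scan should be assessed at the end-of-treatment visit (Protocol 4.3), so k may be small or zero.
- Outside the Efficacy set, the row could serve an unscanned withdrawal without failure in the by-subject PFS listings, so restricting it is better than deleting it.
- PFS and iPFS are exploratory and descriptive. These subjects stay in the ORR denominator.

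None of this removes the contradiction. For iPFS, Table 7 also lacks the no-scan fallback that Table 6 has. Its two dates may be run together by the text extraction, but no condition separates them.

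**Conclusion.** The point holds as an unresolved contradiction with a possible upward bias, not as a demonstrated one. In the Efficacy set, every subject who meets the no-scan row is also an event under the SAP's own definition, and no precedence is stated.

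If the event rows are followed, the bias is nil and the row is empty in this set. If the censoring row is followed, each unscanned early failure raises PFS before the first scan by 1/n (9.1 points for n = 11, 5.6 points for n = 18), and later values are multiplied by the factors shown above. Those sizes rest on the assumed k, on the planned cohort sizes, and on no other earlier event or censoring.

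It should be corrected before analysis because the remedy is nearly free and follows the SAP's own event definition. It does not touch the primary endpoint.

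**What to change.** In SAP Tables 6 and 7:
- Restrict the row to *no post-baseline tumor assessment and no death or clinical progression*.
- State that the event rows take precedence over this row.
- For subjects with no post-baseline scan, date death at the date of death and clinical progression at the date of clinical progression in both tables. In Table 7 this replaces the two run-together dates for this case.
- State that the last tumor assessment means a post-baseline one.

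Leave the Table 6 dating rule unchanged for clinical progressors who do have a post-baseline scan. A blanket rule dating every early clinical progression at its own date would contradict it.

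The cost is one row in each table and a few sentences, with no new data. The downside is that PFS and iPFS may look slightly less favourable than under Day 1 censoring.
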